12.3 Replacement of Participants

While it is estimated that 24 is a suitable sample size for this study, the actual study sample size of 26 allows for a 10% drop out rate. Therefore, up to two participants who withdraw from the study will be replaced.

15 Protocol Violations

A protocol violation occurs when the participant, investigator, or Sponsor fails to adhere to significant protocol requirements affecting the inclusion, exclusion, participant safety and primary endpoint criteria.

Failure to comply with Good Clinical Practice (GCP) guidelines will also result in a protocol violation. The Sponsor will determine if a protocol violation will result in withdrawal of a participant.

When a protocol violation occurs, it will be discussed with the investigator and a Protocol Violation Form detailing the violation will be generated. This form will be signed by a Sponsor representative and the Investigator. A copy of the form will be filed in the site's regulatory binder and in the Sponsor's files.

16 Protocol Amendments

Amendments to the clinical investigation plan must be submitted to the Sponsor for review before submitting to the appropriate IRB for approval.

17 Statistical Methods and Considerations

Only participants who fulfil the protocol in terms of eligibility, interventions and outcome assessment will be included in the statistical analysis. Patient variables will be presented using means and standard deviations for continuous normally distributed variables, medians and interquartile ranges for continuous non-normally distributed variables, and proportions and absolute numbers for categorical variables.

Adverse event rates will be coded by body system and MedDra classification term. Adverse events will be tabulated by treatment group and will include the number of patients for whom the event occurred, the rate of occurrence, and the severity and relationship to study treatment.

Study results will first undergo descriptive level statistical analyses. For continuous variables, Two-way, Student's t-tests will then be carried out using unequal variances where the variables are normally distributed. Tests for normality will be carried out using the Shapiro-Wilk method. Variables that are not normal in distribution that also cannot be log transformed to a normal distribution curve will be analysed using the Mann-Whitney U test or other non-parametric methods to be determined based on actual data distributions.

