In the second level of analysis, we will quantify the magnitude to which abdominal NMES exhibits a protective effect. Crude and adjusted linear regression models will be carried out where the outcome variable is continuous and the covariates are normally distributed or categorical. Our prior experience with measures of respiratory function, which will be measured in this study, indicate that select covariates may need to be controlled for or otherwise do not always fit a normal distribution. Therefore, crude and adjusted generalized linear models are anticipated. These regression models will be carried out at the point of successful wean. All multiple regression covariates, linear or generalized, will be assessed for interaction, collinearity and confounding. For all unadjusted and adjusted multinomial models the overall model log likelihood ratio and Hosmer and Lameshow goodness-of-fit will be conducted to ensure models report significance and are not over fitted. Adjusted regression models will undergo sensitivity analysis and bootstrap analyses. Bootstrap analysis is a re-sampling strategy to estimate the population parameter of interest based on the observed, sample data.

The number of tries to successful wean will be quantified using Poisson regression. Crude and adjusted models will be carried out. Kaplan-Meier survival analysis will be carried out to quantify differences in the time to wean in the treatment abdominal NMES modality compared to the control. As the patients will be resident in hospital facilities, we do not anticipate significant methodological concerns with respect to censoring.

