17.1 Sample Size

This study is intended to be a pilot study that will be used to obtain initial data on the feasibility and safety of VentFree to assist in the process of ventilator weaning. The primary outcome of this study is the effect of abdominal NMES on respiratory muscle strength over time. There is currently no data in the literature to support a sample size calculation for this study. Given this constraint, in this pilot study a total of 24 participants was deemed adequate and is consistent with sample size recommendations in the literature.¹ Allowing for a 10% drop out rate, up to 26 participants will be recruited for this study. The data collected on the secondary endpoints will be used to determine the participants needed for a future randomized controlled trial of the device on weaning outcome.

18 Data Collection, Retention and Monitoring

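### Section 17 makes linear regression depend on normally distributed covariates, a condition that neither linear regression nor a generalized linear model has, so adjusted effects could change model or scale for no valid reason

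*Combined protocol and SAP*

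**What the plan says.** Section 17 (Statistical Methods and Considerations) has two levels of analysis after the descriptive summaries. The first compares the arms by t-test or a non-parametric test. The second uses regression, and its purpose is given as: "we will quantify the magnitude to which abdominal NMES exhibits a protective effect".

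For that second level the plan sets this condition: "Crude and adjusted linear regression models will be carried out where the outcome variable is continuous and the covariates are normally distributed or categorical". It then reports prior experience that, for measures of respiratory function, "select covariates may need to be controlled for or otherwise do not always fit a normal distribution", and concludes: "Therefore, crude and adjusted generalized linear models are anticipated".

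No adjustment covariate is named, and no family or link is given for the generalized linear models. No check of residual distribution, residual variance or linearity is described for continuous outcomes; the named fit checks are attached to multinomial models. The only normality test in the section, "Tests for normality will be carried out using the Shapiro-Wilk method", belongs to the choice between t-test and Mann-Whitney test. The synopsis mentions regression models but gives no criterion for choosing among them.

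**The concern.** The rule inspects the wrong quantity. Whether a linear model suits a continuous outcome depends on that outcome given the covariates: the form of the relation, the spread of the residuals and, in small samples, their shape. A skewed covariate with well-behaved residuals is no reason to leave linear regression. A normal covariate with badly skewed residuals would pass the rule and should not.

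The remedy does not match the diagnosis either, because a generalized linear model relaxes assumptions about the outcome and leaves the covariates as they were.

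What is at stake is the adjusted estimate of the effect on the continuous outcomes, including the primary ones, MIP and MEP. With family and link open, an irrelevant check could move that estimate from a difference to a ratio after the data are seen. Section 5 says that the study, if feasible, will be used to design a follow-up trial, so the scale of a reported effect has a later use.

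**Working it through.** **1. Plan figures.** No figure in the plan depends on this rule, so there is none to reproduce for the point itself. The nearest is the sample size in section 17.1: "a total of 24 participants was deemed adequate and is consistent with sample size recommendations in the literature", and "Allowing for a 10% drop out rate, up to 26 participants will be recruited for this study". Inflating for dropout gives 24 / (1 − 0.10) = 26.7, which rounds up to 27 against the stated 26. The one-patient gap has no bearing here. The 24 (12 per arm, section 6) is used below.

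**2. What each model assumes.**
- Linear regression: y = Xβ + e, with estimate b = (XᵀX)⁻¹Xᵀy. Given X, b is unbiased if the errors have mean zero, and t-tests are exact if the errors are also independent and normal with constant variance. The distribution of the columns of X does not enter.
- Generalized linear model: y given X follows a chosen family, with g(E[y | X]) = Xβ. The distribution of X again does not enter.

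The plan's trigger is therefore a condition of neither model.

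**3. Illustration.** Simulation with 12 per arm and y = 0.5x + (arm effect) + e, where e is normal with SD 1. The arm effect is 0 for type I error and 1 SD for coverage and power. Tests are two-sided at 5% on 24 − 3 = 21 degrees of freedom, with 20,000 runs per row. The slope, error SD and effect are assumptions, since the documents give none.

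| Covariate x | Type I error | 95% CI coverage | Power | Shapiro-Wilk rejects x |
|---|---|---|---|---|
| Normal | 5.3% | 94.7% | 62.6% | 5.0% |
| Log-normal, log-SD 1 | 5.1% | 94.9% | 62.7% | 96.9% |
| Exponential | 5.2% | 94.8% | 62.5% | 91.0% |

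The Monte Carlo standard error of a 5% rate is √(0.05 × 0.95 / 20,000) = 0.15 percentage points. The agreement across rows confirms step 2 and is not separate evidence: with normal errors the test is exact by construction.

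**4. What could change.** One simulated data set (y = 40 + 8·arm + 3x + error with SD 8; x log-normal with log-SD 0.8; n = 24), analysed three ways:
- Linear regression: arm effect 9.52 units.
- Generalized linear model, Gaussian family, identity link: 9.52 units, the same.
- Generalized linear model, gamma family, log link: coefficient 0.190, so a ratio of exp(0.190) = 1.21.

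A switch may thus change nothing, or change the scale of the effect. The plan does not say which.

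**5. How often the rule would be triggered.** This depends on a procedure that the plan does not give. Suppose the Shapiro-Wilk test is borrowed from the first-level analysis and applied to one log-normal covariate (n = 24, 4,000 runs, log-SD 0.5, 0.8 and 1.0):
- Raw covariate rejected: 61%, 91% and 97%.
- Raw and logged versions both rejected, which follows the log-transform step that accompanies that test in section 17: 3.4%, 3.6% and 3.9%.

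The text extends neither the test nor the log step to regression covariates, so neither set of figures describes the plan.

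**The case against.** **The sponsor may have meant the outcomes.** The reason given is experience with measures of respiratory function, and MIP, MEP and cough peak flow are outcomes here. A skewed outcome can justify a generalized linear model. This is plausible, but the criterion sentence treats outcome and covariates separately and attaches normality to the covariates. Under this reading the text still needs correcting.

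**The effect is limited.** This stands. Study arm is categorical, so the crude arm-only linear model always meets the criterion. A Gaussian model with identity link is the linear model under another name. The plan says that generalized linear models are anticipated, not that they replace linear ones. The analysis is second-level, in a 24-patient pilot with no power calculation.

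**Sensitivity and bootstrap analyses are planned.** They apply to the adjusted model once it is chosen, and do not repair the rule that chooses it.

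A reader might also infer more than the documents support:
- *That linear regression would be abandoned in most trials.* This takes the test from the first-level analysis and leaves out the log-transform step stated with it. With that step the rate falls to about 4%.
- *That a strong prognostic covariate would be left out.* The stated response to non-normality is a different model, not removal of the covariate.
- *That crude and adjusted effects would not be comparable.* The plan foresees a crude and adjusted pair for each model type.
- *That generalized linear models should be barred for continuous outcomes.* One may suit a skewed or bounded outcome, such as time spent off the ventilator.

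**Conclusion.** The point holds as a fault in the stated criterion. Covariate normality is not a condition for linear regression, and a generalized linear model does not address its absence. This follows from the definition of the two models and does not rest on the simulation.

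The consequence is a possibility, confined to adjusted models of continuous outcomes: the model or effect scale could change for an irrelevant reason. Its frequency is unknown, because the covariates, the test applied to them, and the family and link are all unspecified. The 9.52-unit difference and the 1.21 ratio show a change of scale under assumed values; they are not a forecast for this trial. Nor do the simulations show bias or an inflated error rate under the plan's route, since repeated trials were simulated only for the linear model. The correction is worth making because the rule is wrong as written and cheap to put right.

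**What to change.** Replace the criterion in section 17 with wording such as:

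> For continuous outcomes, crude and adjusted treatment effects will be estimated by linear regression whatever the distribution of the covariates; covariates may be transformed for linearity or leverage only. Adequacy will be judged from the model residuals (distribution, variance, linearity). A generalized linear model will be used only where the conditional distribution of the outcome calls for it, with its family and link stated in advance.

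Delete the sentence that derives generalized linear models from non-normal covariates or, if the outcomes were meant, reword it to say so.

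The cost is a minor text change and routine residual diagnostics. No extra data or patients are needed.

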Patients will participate in a Stimulation Visits 2 times per day in 5 days every week. Specifically, patients will participate in morning and afternoon Stimulation Visits 5 times between days 24 and 30, 5 times between days 31 and 37 and 5 times between days 38 and 44.

The stimulation session will then continue as described in Section 9.6. In addition, the investigators will record adverse events related to stimulation or otherwise.

12.5 Final Visit – Day 45

The Final Visit will ideally take place on day 45. However, if necessary the Final Visit may be moved no earlier than day 43, providing that it occurs 15 Stimulation Visits after the Intermediate Visit, and no later than day 47.

During this visit the investigators will record the participant's MEP, MIP, thickness of the abdominal wall muscles and diaphragm, CPF, resting breathing parameters and adverse events related to stimulation or otherwise.

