12.6 Early Withdrawal Visit

In the case that the patient withdraws or is withdrawn from the protocol (see Section 14) before the end of the intervention period, and providing the patient consents, then the investigators will perform and record the participant's MEP, MIP, thickness of the abdominal wall muscles and diaphragm, CPF, resting breathing parameters and adverse events related to stimulation or otherwise.

If the participant is withdrawn from the study because they have successfully weaned from mechanical ventilation then the study researcher will also calculate and record the number of days taken to wean taken from the institution of mechanical ventilation.

13 Adverse Experience Reporting and Documentation

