14.1 Withdrawal of Participants from the Study

A participant may be withdrawn from study treatment at any time if the participant, the investigator, or the Sponsor feels that it is not in the participant's best interest to continue. The following is a list of possible reasons for study treatment discontinuation:

- Successful weaning from mechanical ventilation
- Participant withdrawal of consent
- Participant is not compliant with study procedures
- Adverse event that in the opinion of the investigator would be in the best interest of the participant to discontinue study treatment
- Protocol violation requiring discontinuation of study treatment
- Lost to follow-up
- Sponsor request for early termination of study
- Positive pregnancy test (females)

If a participant is withdrawn from treatment due to an adverse event, the participant will be followed and treated by the PI until the abnormal parameter or symptom has resolved or stabilized.

All participants who discontinue study treatment should come in for an early discontinuation visit as soon as possible.

All participants are free to withdraw from participation at any time, for any reason, specified or unspecified, and without prejudice. This will not affect the care they receive, now or in the future.

Reasonable attempts will be made by the investigator to provide a reason for participant withdrawals. The reason for the participant's withdrawal from the study will be specified in the participant's source documents.

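### The regression models that size the stimulation effect are timed at successful weaning, so participants who never wean have no defined value in them

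*Combined protocol and SAP*

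**What the plan says.** Section 17 (Statistical Methods and Considerations) plans two levels of analysis. At the first, continuous variables are compared between arms: "t-tests will then be carried out using unequal variances where the variables are normally distributed", with a Mann-Whitney or other non-parametric test otherwise. No visit is named for these tests, and no use of the baseline value. At the second level, crude and adjusted linear or generalised linear models are to quantify how large the benefit is. Their only stated time point is "These regression models will be carried out at the point of successful wean". The synopsis repeats the second level without a time point.

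The other relevant provisions are these.

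- Section 7.2 defines weaning success as an event: 72 hours breathing unaided. It is a secondary outcome.
- Section 6 ends stimulation at weaning or at six weeks, whichever comes first, and places evaluations at baseline, three weeks and end of treatment. Section 3 accepts that some patients never wean.
- Section 12.5 schedules, at the Final Visit, "MEP, MIP, thickness of the abdominal wall muscles and diaphragm, CPF, resting breathing parameters and adverse events related to stimulation or otherwise".
- Section 12.6 covers participants who stop "before the end of the intervention period, and providing the patient consents, then the investigators will perform and record" the same measures. It treats weaners as a case of this: "If the participant is withdrawn from the study because they have successfully weaned from mechanical ventilation".
- Section 14.1 lists "Successful weaning from mechanical ventilation" among the reasons for stopping treatment and adds: "All participants who discontinue study treatment should come in for an early discontinuation visit as soon as possible".
- Section 17 also restricts the analysis set: "Only participants who fulfil the protocol in terms of eligibility, interventions and outcome assessment will be included in the statistical analysis".

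**The concern.** The primary objective concerns respiratory muscle strength in patients on prolonged ventilation, not only in those who come off the ventilator. A participant who reaches six weeks still ventilated has no point of successful weaning. Section 17 gives no rule for that participant: no Day 45 value, no imputation, and no explicit restriction to weaners.

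If the sentence is followed as written, the effect estimate is conditional on something that happens after randomisation and that the device is meant to improve. Weaners in the two arms need not be alike in the strength they would have had untreated, so the difference between them is not the randomised comparison. The sample, already 24, also shrinks to the weaners. If the sentence is not followed as written, the plan does not say what replaces it, and two analysts could report different effect sizes from the same data.

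A related gap is that section 12.6 calls weaners withdrawn from the study, while the analysis set is limited to participants who fulfil the protocol. Nothing says that participants who stop early because they weaned are kept.

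**Working it through.** **What the plan gives.** Sections 6 and 17.1 give 24 evaluable participants, 12 per arm. This is a pilot rule of thumb, with no effect size, SD or power to reproduce. The plan gives no weaning rate either. Everything below other than the 24 is therefore an assumption, shown as a range, and applies only to the second-level models read literally.

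**Model.** Let A = 0 for control and 1 for active. Final strength is S = U + d·A, with U ~ N(0,1) the untreated strength in SD units and d = 0.8. A latent weaning score is L = r·S + √(1 − r²)·e, with e ~ N(0,1) independent of U. A participant weans if L > c, where c = Φ⁻¹(1 − p) and p is the proportion of controls who wean. Treatment acts on weaning only through strength.

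**Bias among weaners.** With a = c − r·d·A,

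E[U | weaned] = r·φ(a) / (1 − Φ(a)),

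and the apparent effect is d + E[U | weaned, active] − E[U | weaned, control].

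For p = 0.5 and r = 0.5, c = 0:

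- Control: a = 0, so 0.5 × 0.3989 / 0.5 = 0.399.
- Active: a = −0.4, so 0.5 × 0.3683 / 0.6554 = 0.281.
- Apparent effect: 0.8 + 0.281 − 0.399 = 0.682.
- Expected weaners: 12 × (0.5 + 0.6554) = 13.9 of 24.

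**Precision.** With all 24, the median 95% half-width for a crude arm comparison is 2.074 × √(2/12) × √(21.337/22) = 0.83 SD. With 10 per arm it is 2.101 × √(2/10) × √(17.338/18) = 0.92 SD. The weaners-only half-widths come from simulating the model above, 60,000 trials per row. Trials with fewer than two weaners in an arm were left out of them: under 0.5% at p = 0.5, 9 to 11% at p = 0.3, and essentially none at p = 0.7.

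| Controls weaning | r | Apparent effect (true 0.8 SD) | Expected weaners of 24 | Median half-width (SD) |
|---|---|---|---|---|
| 50% | 0.3 | 0.756 | 13.1 | 1.17 |
| 50% | 0.5 | 0.682 | 13.9 | 1.08 |
| 50% | 0.7 | 0.577 | 14.5 | 0.97 |
| 30% | 0.3 | 0.749 | 8.3 | 1.56 |
| 30% | 0.5 | 0.660 | 9.0 | 1.40 |
| 30% | 0.7 | 0.531 | 9.8 | 1.21 |
| 70% | 0.3 | 0.766 | 17.7 | 0.97 |
| 70% | 0.5 | 0.710 | 18.3 | 0.92 |
| 70% | 0.7 | 0.632 | 18.7 | 0.86 |

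At p = 0.5 the bias is 0.04 to 0.22 SD, and 24 − 14.5 = 9.5 to 24 − 13.1 = 10.9 participants are left out.

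**Baseline adjustment among weaners** does not remove the bias. At p = 0.5 the estimates are 0.77, 0.71 and 0.62 SD if baseline correlates 0.5 with untreated final strength, and 0.78, 0.735 and 0.67 SD if it correlates 0.7. Using all 24 with baseline as covariate recovers 0.80 SD in this model, with half-width 0.74 SD (correlation 0.5) or 0.61 SD (0.7). The model has no time dimension, so that result does not cover assessment days that differ between participants.

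**Sensitivity to the mechanism.** Add an assumed direct arm effect of −0.6 on L, so that a = c − r·d·A + 0.6·A. For p = 0.5 and r = 0.5 the active arm has a = 0.2, giving 0.5 × 0.3910 / 0.4207 = 0.465, and the apparent effect is 0.8 + 0.465 − 0.399 = 0.87. Across r = 0.3, 0.5 and 0.7 it is 0.87, 0.87 and 0.82 SD: an overstatement.

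**The case against.** The strongest reply is that the sentence only means end of treatment. Section 6 uses that phrase for the evaluations and ends treatment at weaning or six weeks, and strength is measured in both kinds of participant. For weaners the two points nearly coincide, apart from the 72-hour definition and the promptness of the early visit. This reading is plausible, and under it none of the loss above arises. It is not what section 17 says, however, and it is exactly for non-weaners that the two phrases differ.

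A reader might infer three stronger things that the documents do not support.

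- *Non-weaners have no outcome data.* They do: section 12.5 and Appendix A schedule MIP and MEP at Day 45. The gap is in the analysis definition.
- *All analysis of the primary outcome is restricted to weaners.* The first-level tests are not tied to weaning. They do not close the gap, because they name no visit.
- *The estimate must be biased toward zero.* That follows only if treatment affects weaning solely through strength. The sensitivity check shows the direction can reverse, and with no effect of treatment on strength or on weaning there is no bias.

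It is also fair to say that this is a pilot without a power calculation and that the bias is small beside the confidence half-width. That stands. The larger cost is the participants left out. Section 5 intends the study, if feasible, to inform the design of a follow-up trial, so the population behind the effect estimate should be settled.

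**Conclusion.** The point holds as a defect of definition with a real consequence under the literal reading. The only time point given for the models that quantify the effect does not exist for participants who do not wean, and no other section supplies one. This conclusion needs no numerical assumption.

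Its size does. With 50% of controls weaning and correlations of 0.3 to 0.7, a true 0.8 SD effect appears as 0.76 to 0.58 SD, about 9 to 11 of 24 participants are lost, and the half-width is about 1.0 to 1.2 SD instead of 0.83 SD. Control weaning rates of 30% and 70% widen the range of apparent effects only to 0.53 to 0.77 SD, but the number of weaners moves between about 8 and 19. The weaning rates, correlations, effect size and mechanism are all assumed. If the sponsor confirms that end of treatment was meant, the numerical loss disappears and only the wording needs correcting. It should be corrected before analysis.

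**What to change.** Replace the timing sentence in section 17 with:

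> Regression models for MIP, MEP and the other continuous outcomes measured at the study visits will use the end-of-treatment value (Final Visit, or Early Withdrawal Visit for those who stop earlier, weaned or not) in all randomised participants with that measurement, with the baseline value of the same measure as a covariate.

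In addition:

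- Apply the same time point to the first-level tests.
- State that participants who stop because they weaned are not excluded by the per-protocol sentence.
- Count participants whose only post-baseline value is Day 23 as missing at end of treatment, and report missing values and deaths by arm.
- Report the Day 23 comparison as a supporting analysis. The end-of-treatment day depends on weaning, whereas Day 23 is a common day (within its visit window) for those still in the study.
- Reconcile section 12.6, which lists muscle thickness at the Early Withdrawal Visit, with Appendix A, which does not mark it there.

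No new visits are needed for MIP and MEP: both are already scheduled at baseline, Day 23, Day 45 and early withdrawal. The costs are one degree of freedom per model for baseline, assessment days that differ between participants (so the estimate is the effect at end of treatment, not at six weeks), and some missing values because the early visit depends on consent.

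### Model checks in section 17 aim at significance, and the MIP/MEP regressions have no fixed covariates or primary model, which leaves room to choose a model by its p-value

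*Combined protocol and SAP*

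**What the plan says.** Section 17 (Statistical Methods and Considerations) plans two levels of analysis after the descriptive summaries.

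- **Group comparisons.** The rule is ordered. "Tests for normality will be carried out using the Shapiro-Wilk method", and "Student's t-tests will then be carried out using unequal variances where the variables are normally distributed". A log transform is tried next, then Mann-Whitney or "other non-parametric methods to be determined based on actual data distributions".
- **Regression.** Crude and adjusted linear models are planned, and generalized linear models are anticipated. On covariates, the plan says only that "select covariates may need to be controlled for or otherwise do not always fit a normal distribution". Then: "All multiple regression covariates, linear or generalized, will be assessed for interaction, collinearity and confounding". No covariate is named and no rule for keeping one is given. The regressions are placed at the point of successful wean. Adjusted models also get sensitivity and bootstrap analyses.
- **Model checks.** "For all unadjusted and adjusted multinomial models the overall model log likelihood ratio and Hosmer and Lameshow goodness-of-fit will be conducted", and the stated purpose is "to ensure models report significance and are not over fitted".

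MIP and MEP are the primary outcome (section 7.1). Both are measured at the Baseline, Intermediate and Final Visits (section 11.9) and at Early Withdrawal (section 12.6 and Appendix A).

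**The concern.** Three things come together.

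1. The purpose given for the checks is wrong. A well-specified model of an ineffective treatment should usually be non-significant, and an over-fitted model can easily be significant. Hosmer-Lemeshow answers a different question, the calibration of a binary-outcome model. The one binary outcome, weaning success, is assigned to Poisson regression in the synopsis.
2. Nothing fixes which regression carries the conclusion for MIP or MEP. The number and identity of covariates, their retention and the choice between crude and adjusted results are all open.
3. The obvious covariate is missing. The baseline value of the same measure is collected before the first stimulation session, yet it is not named.

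The primary objective (section 5) is to determine whether stimulation increases respiratory muscle strength, so a claim about effect is intended. If the reported model can be chosen after its p-value is known, that claim has no known error rate and the estimate is likely to be too large.

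**Working it through.** **Sample size.** Section 17.1 gives 24 participants and allows 10% dropout. 24 / 0.9 = 26.7, which rounds up to 27; the plan states 26, within rounding. With 26 recruited, 26 × 0.9 = 23.4 are expected to remain. Section 17 keeps only protocol-compliant participants, and the regressions are set at successful wean, so the fitted number may be smaller. The checks below use 12 per arm.

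**Assumptions.** The documents state no alpha, covariate number or correlation. I assume two-sided 0.05, K = 1, 3 or 5 independent candidate covariates, and no treatment effect. Two settings are used:

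- A: one covariate explains 30% of the outcome variance and the rest explain none.
- B: every covariate correlates 0.3 with the outcome, so K × 0.09 of the variance is explained (45% at K = 5).

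**Open covariate choice, worst case.** K candidates give 2^K possible models: 2, 8 and 32. A false positive is counted if any of them gives treatment p < 0.05. The ranges come from repeated runs of 3,000 to 6,000 simulated trials.

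| K | One fixed model | Any subset, setting A | Any subset, setting B |
|---|---|---|---|
| 1 | about 5% | 7.4% | 6.4–7.2% |
| 3 | about 5% | 10.2–11.1% | 10.7–10.9% |
| 5 | about 5% | 13.8–14.0% | 18.6% |

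With 3,000 trials, the simulation standard error is √(0.05 × 0.95 / 3000) = 0.4 percentage points at 5%, and √(0.186 × 0.814 / 3000) = 0.7 points at 18.6%.

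**Confounder screening alone.** Keeping a covariate when it moves the treatment estimate by more than 10% gives about 4.5% to 6.5%, depending on how the rule is implemented. Screening that ignores the p-value therefore does little harm to the error rate.

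**Overall significance as a reporting filter.** The plan does not state this; it shows what the wording would do if used that way. An overall F-test at 0.05 stands in for the likelihood-ratio test, in setting B.

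| Fixed covariates | Models passing | Passing models with a false treatment effect |
|---|---|---|
| 0 | 4.7% | 100% |
| 1 | 22.8% | 16.2% |
| 3 | 50.7% | 8.4% |

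Over all trials, the false-positive rate does not rise: 0.228 × 0.162 = 3.7% and 0.507 × 0.084 = 4.3%. What rises is the share of false effects among the models that would be reported.

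**Normality-based test rule.** Applied as written, with Shapiro-Wilk at an assumed 0.05 in each arm, it gives 4.9% for normal data and 5.3% for log-normal data. Taking the smallest of the Welch, log-scale and Mann-Whitney p-values gives only 5.7% and 6.1%.

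**The case against.** The strongest reply is that the sentence about significance reaches no primary analysis. It is confined to multinomial models, none is listed, and MIP and MEP are continuous. It may simply be a loosely worded overall-fit check, since the same clause also guards against over-fitting. Crude and adjusted models are both planned, with sensitivity and bootstrap analyses. The subset search simulated above is not written anywhere, and its size depends on assumed inputs. This is also a pilot without a stated alpha, and section 17.1 takes the next trial's size from the secondary endpoints.

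Much of this stands. A reader might infer that the plan keeps significant models and discards the others. The documents do not support that: nothing says a non-significant model will be dropped, refitted or left unreported. A reader might also infer that the choice of group-comparison test is a source of bias. It is not a material one: the rule depends on distribution, not on p-values, and stays near 5%. Only its last branch is open.

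The reply does not remove the gap. If the multinomial sentence governs nothing, it should be deleted; if it loosely means the surrounding regressions, it sets the wrong criterion for them. On either reading, the MIP and MEP regressions have no fixed covariates and no primary model. Bootstrap and sensitivity analyses do not settle which model counts. That the next trial's size comes from secondary endpoints limits the damage there, but it does not protect the primary objective.

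**Conclusion.** The point holds as a fault of specification with a poorly chosen criterion, not as evidence of a rule that selects positive results. The plan permits and invites choice by significance; it does not prescribe it. The worst case is a rise from about 5% to 6–8% with one candidate covariate, 10–11% with three and 14–19% with five. These figures rest on an assumed two-sided alpha of 0.05, 12 per arm, independent covariates of the assumed strength, and a search on the treatment p-value. Without such a search, confounder screening gives about 6% and the normality-based rule is close to nominal. In a pilot, the consequence is for the credibility of the reported MIP and MEP effects, not for a confirmatory error rate. The change is worth making because a better method is available at almost no cost.

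**What to change.** - For MIP and for MEP, name one primary linear model: the end-of-treatment value (Final or Early Withdrawal Visit) on arm and the baseline value of the same measure. Report the arm effect with its 95% CI whatever the p-value.
- State that, for these two endpoints, this replaces the point of successful wean as the analysis time. As written, that time point lets only weaned participants contribute.
- Name one rank-based or permutation analysis as the sensitivity analysis, in place of the open last branch of the test rule.
- Delete the sentence on multinomial models, Hosmer-Lemeshow and significance.
- Label all other adjusted models exploratory.

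The cost is a few lines of wording and less analysis work. The baseline term uses one degree of freedom (with 24 participants, 24 − 3 = 21 residual degrees of freedom instead of 22), and the choice of model after seeing the data is given up.
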